**11.3.1.6 Summary of Serious Adverse Events**

All subjects reporting treatment-emergent serious AEs (SAEs) will be summarised by treatment in Part 2, and by all placebo, all active and each dose level in Part 1 and Part 3. Counts will be given for number of subjects and number of events. Subjects experiencing more than 1 SAE within a treatment will be counted only once for number of subjects but will be counted more than once for number of events.

Additionally, subjects reporting treatment-emergent SAEs will be summarised for SOC and PT by treatment in Part 2, and by all placebo, all active and each dose level in Part 1 and Part 3. Counts will be given for number of subjects and number of events. Subjects experiencing more than 1 episode of a SAE within a will be counted only once within each SOC and PT using the most severe episode.

**11.3.2 Listings for Adverse Events**

All pre-dose AEs (as defined in [Section 11.3](#)) will be listed including SOC and PT.

**Sponsor/Quotient Sciences Confidential**

---

A separate data listing of all TEAEs will be provided including the SOC and PT. In addition, a listing of all SAEs will be provided.

#### **11.4 Laboratory Evaluations**

The details of sample collection for laboratory safety analysis are described in the study protocol.

Where a value is provided by the safety laboratory as either above or below the limit of detection (LOD) this will be set to the respective LOD itself for descriptive summaries. No imputations will be made in the individual listings.

##### **11.4.1 Summary Tables for Laboratory Evaluations**

For each study part, haematology, coagulation and clinical chemistry data will be summarised (n, mean, SD, median, minimum and maximum) for each laboratory parameter at each time point, including changes from baseline (Admission, Day-1) at each scheduled post-baseline time point by treatment in Part 2, and by all placebo, all active and each dose level in Part 1 and Part 3.

Shift tables from baseline to each scheduled post-baseline time point (with respect to the number and percentage of subjects with values below, within or above the reference range) will be presented by treatment in Part 2, and by all placebo, all active and each dose level in Part 1 and Part 3. Percentages will be based on the number of subjects with measurements at baseline and the relevant post-baseline time point.

For fasting-sensitive laboratory parameters (i.e., glucose) results taken in the non-fasted state (i.e., LBFAST=N) will not be included in summary statistics by time point or be used in derivations of changes from baseline. For tabulations (e.g., shift tables) both fasted and non-fasted results will be pooled and used in the tabulations, using the appropriate fasted or non-fasted reference range. All results (fasted or non-fasted) will be listed with non-fasted data flagged.

Reference ranges for each laboratory parameter will be presented for the relevant parameter in each summary table.

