### **8.1.2 Study Plan: Part 2 – Food Effect Cohort**

[figure not shown]
Part 2 will be an open-label, randomised, balanced two-period crossover, food effect evaluation. The effect of food on the PK of MMV367 will be explored in Part 2 by administering a single dose of MMV367 after a high-fat breakfast, as per FDA guidance ([Appendix 8](#)), and a single dose of MMV367 in the fasted state.

Each participant will receive 2 single doses of MMV367. In Period 1, participants will be randomised to 1 of 2 treatment sequences (Regimen 6/Regimen 7 or Regimen 7/Regimen 6). If a participant is randomised to receive MMV367 in the fasted state (Regimen 6) in Period 1, they will receive MMV367 in the fed state (Regimen 7) in Period 2 and vice versa.

It is planned to enrol 8 healthy male and female participants to ensure data in a minimum of 6 participants. A participant will be considered evaluable if they have received study drug and completed safety and PK assessments up to 96 h post-dose in both periods.

Participants will be dosed on Day 1 (Period 1 dose) and on Day 8 (Period 2 dose) and will remain resident in the clinical unit until discharge on Day 12. They will attend the clinical unit on Day 14 ( $\pm$  1 day) for end of study assessments. Based on emerging PK data from Part 1, the washout period between the Period 1 and Period 2 doses may be extended. Blood samples will be collected at regular intervals for PK analysis and safety from Day 1 to the end of study visit on Day 14 ( $\pm$  1 day), as detailed in [Appendix 3](#).

The study design for Part 2 is presented in [Figure 2](#).

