### 3.2.3 Definition of Visits

For clinical data, visits will be referred to as Day throughout this document, and each Day will be stated as screening, Day -1 (Admission), with the following duration based on study Part:

- Part 1: Day 1 through to Day 5, with a return visit on Day 7 and an end of study visit on Day 15
- Part 2: Day 1 through to Day 7 Period 1, and Day 8 through to Day 12 in Period 2, with an end of study visit on Day 14 (The actual dosing days within Period 2 may change if the washout period is extended – see Section 8.1.2 of the study protocol)
- Part 3: Day 1 through to Day 7, with a return visit on Day 9 and an end of study visit on Day 17.

Time points within these days are detailed in the schedule of assessments for each study part [Appendix 4](#) (Part 1), [Appendix 5](#) (Part 2) and [Appendix 6](#) (Part 3).

Baseline is defined as nominally the last measurement recorded prior to the first dose of IMP, for each dosing period.

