### 5.1.2 Part 2 – Food Effect Cohort

Part 2 will be an open-label, randomised, balanced two-period crossover, food effect evaluation. The effect of food on the PK of MMV367 will be explored in Part 2 by administering a single dose of MMV367 after a high-fat breakfast, as per FDA guidance, and a single dose of MMV367 in the fasted state.

Each participant will receive 2 single doses of MMV367. In Period 1, participants will be randomised to 1 of 2 treatment sequences (Regimen 6/Regimen 7 or Regimen 7/Regimen 6). If a participant is randomised to receive MMV367 in the fasted state (Regimen 6) in Period 1, they will receive MMV367 in the fed state (Regimen 7) in Period 2 and vice versa. It is planned to enrol 8 healthy male and female participants to ensure data in a minimum of 6 participants.

Participants will be dosed on Day 1 (Period 1 dose) and on Day 8 (Period 2 dose) and will remain resident in the clinical unit until discharge on Day 12. They will attend the clinical unit on Day 14 ( $\pm 1$  day) for end of study assessments. Based on emerging PK data from Part 1, the washout period between the Period 1 and Period 2 doses may be extended. Blood samples will be collected at regular intervals for PK analysis and safety from Day 1 to the end of study visit on Day 14 ( $\pm 1$  day), as detailed in [Appendix 3](#). The study design for Part 2 is presented in [Figure 2](#).

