### 11.5.1 Summary Tables for Vital Signs

For each study part, vital signs data (including orthostatic measurements), and change from baseline (Pre-dose, Day 1 (Period 1), Day 8 (Period 2), will be summarised (i.e., n, mean, SD, median, minimum and maximum) at each post-baseline time point by treatment in Part 2, and by all placebo, all active and each dose level in Part 1 and Part 3.

In addition, the number of subjects with 'substantial' increases or decreases or no substantial change from baseline in systolic BP (>20 mmHg), diastolic BP (>10 mmHg) and heart rate (>15 bpm) will be summarised.

Orthostatic hypotension will also be investigated at each time point. The change in systolic BP and diastolic BP between the mean of the duplicate supine measurements and the subsequent standing measurement will be calculated for each subject (i.e., standing BP- Supine BP) and summarised (i.e., mean, SD, median, minimum, maximum and n) at baseline and each post-baseline time point.

In addition, the number of subjects with 'substantial' decreases or no substantial decrease from supine to standing results in systolic BP (>20 mmHg) and diastolic BP (>10 mmHg) will be presented at each time point.

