**Sponsor/Quotient Sciences Confidential**

Medicines for Malaria Venture  
Protocol: MMV\_MMV367\_21\_01

Page x of y

TABLE 14.4.2.1  
Haematology and Coagulation  
Summary Statistics: Safety Analysis Set  
Part 2

<Parameter> (<units>) [ref range xxxx-xxxx (male), xxxx-xxxx (female)]

Treatment	Time Point	Result						Change from Baseline					
		n	Mean	SD	Median	Min	Max	n	Mean	SD	Median	Min	Max
XX mg FAST (N=X)	BASELINE	xx	xx.xx	xx.xx	xx.xx	xx.x	xx.x						
	TIME POINT 1	xx	xx.xx	xx.xx	xx.xx	xx.x	xx.x	xx	xx.xx	xx.xx	xx.xx	xx.x	xx.x
	TIME POINT 2	xx	xx.xx	xx.xx	xx.xx	xx.x	xx.x	xx	xx.xx	xx.xx	xx.xx	xx.x	xx.x
	...	...	...	...	...	...	...	...	...	...	...	...	...
	<All other time points>	xx	xx.xx	xx.xx	xx.xx	xx.x	xx.x	xx	xx.xx	xx.xx	xx.xx	xx.x	xx.x
XX mg FED (N=X)	BASELINE	xx	xx.xx	xx.xx	xx.xx	xx.x	xx.x						
	TIME POINT 1	xx	xx.xx	xx.xx	xx.xx	xx.x	xx.x	xx	xx.xx	xx.xx	xx.xx	xx.x	xx.x
	TIME POINT 2	xx	xx.xx	xx.xx	xx.xx	xx.x	xx.x	xx	xx.xx	xx.xx	xx.xx	xx.x	xx.x
	...	...	...	...	...	...	...	...	...	...	...	...	...
	<All other time points>	xx	xx.xx	xx.xx	xx.xx	xx.x	xx.x	xx	xx.xx	xx.xx	xx.xx	xx.x	xx.x

Note: The data in this table are presented in listing xx

All subjects were to receive both treatments (i.e., Regimen 6 and Regimen 7) in a randomised manner  
over the two separate dosing occasions  
BASELINE is defined as Day -1, Admission

PROGRAM PATH: X:\~\QSC207031\~\TFLS\PRODUCTION\TAB-XX

DDMMYYYY HH:MM

Programming note: This table will be continued for all haematology <and coagulation> parameters and all time points  
A similar table will be produced for Clinical Chemistry, i.e., Table [14.4.2.3]

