**Sponsor/Quotient Sciences Confidential**

Medicines for Malaria Venture  
Protocol: MMV\_MMV367\_21\_01

Page x of y

TABLE 14.4.2.2  
Haematology and Coagulation  
Shift Analysis: Safety Analysis Set  
Part 2

<Parameter> (<units>) [ref range xxxx-xxxx (male), xxxx-xxxx (female)]

Time Point Assessment	N#	XX mg FAST (N=X) Baseline			XX mg FED (N=X) Baseline		
		Below n(%)	Within n(%)	Above n(%)	N#	Below n(%)	Within n(%)
TIME POINT 1	xx				xx		
Below	xx (xx.x)	xx (xx.x)	xx (xx.x)		xx (xx.x)	xx (xx.x)	xx (xx.x)
Within	xx (xx.x)	xx (xx.x)	xx (xx.x)		xx (xx.x)	xx (xx.x)	xx (xx.x)
Above	xx (xx.x)	xx (xx.x)	xx (xx.x)		xx (xx.x)	xx (xx.x)	xx (xx.x)
TIME POINT 2	xx				xx		
Below	xx (xx.x)	xx (xx.x)	xx (xx.x)		xx (xx.x)	xx (xx.x)	xx (xx.x)
Within	xx (xx.x)	xx (xx.x)	xx (xx.x)		xx (xx.x)	xx (xx.x)	xx (xx.x)
Above	xx (xx.x)	xx (xx.x)	xx (xx.x)		xx (xx.x)	xx (xx.x)	xx (xx.x)
<All other time points>	...	...	...	...	...	...	...

Note: The data in this table are presented in listing xx

All subjects were to receive both treatments (i.e., Regimen 6 and Regimen 7) in a randomised manner over the two separate dosing occasions

BASELINE is defined as Day -1, Admission of the corresponding study period

N# indicates the number of subjects with a baseline and a post baseline assessment at the time point indicated  
Below/within/above indicate the n(%)=number(%) of subjects with assessments below/within/above the normal reference range at baseline

PROGRAM PATH: X:\~\QSC207031\~\TFLS\PRODUCTION\TAB-XX

DDMMYYYY HH:MM

Programming note: This table will be continued for all haematology and coagulation parameters and all time points  
A similar table will be produced for Clinical Chemistry, i.e., Table [14.4.2.4]

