**Sponsor/Quotient Sciences Confidential**

Medicines for Malaria Venture  
Protocol: MMV\_MMV367\_21\_01

Page x of y

TABLE 14.5.2.2.1  
ECGs  
Summary Statistics: Safety Analysis Set  
Single 12-Lead  
Part 2

<Parameter> (<units>) [<ref range xxx - xxx (age xx - xx), xxx - xxx (age > xx)> / <ref range xxx - xxx (male), xxx-xxx (female)>]

Treatment	Time Point	Result						Change from Baseline					
		n	Mean	SD	Median	Min	Max	n	Mean	SD	Median	Min	Max
XX mg FAST (N=X)	BASELINE	xx	xx.xx	xx.xx	xx.xx	xx.x	xx.x						
	TIME POINT 1	xx	xx.xx	xx.xx	xx.xx	xx.x	xx.x	xx	xx.xx	xx.xx	xx.xx	xx.x	xx.x
	TIME POINT 2	xx	xx.xx	xx.xx	xx.xx	xx.x	xx.x	xx	xx.xx	xx.xx	xx.xx	xx.x	xx.x
	TIME POINT 3	xx	xx.xx	xx.xx	xx.xx	xx.x	xx.x	xx	xx.xx	xx.xx	xx.xx	xx.x	xx.x
	...	...	...	...	...	...	...	...	...	...	...	...	...
	<All other time points>	xx	xx.xx	xx.xx	xx.xx	xx.x	xx.x	xx	xx.xx	xx.xx	xx.xx	xx.x	xx.x
XX MG FED (N=X)	BASELINE	xx	xx.xx	xx.xx	xx.xx	xx.x	xx.x						
	TIME POINT 1	xx	xx.xx	xx.xx	xx.xx	xx.x	xx.x	xx	xx.xx	xx.xx	xx.xx	xx.x	xx.x
	TIME POINT 2	xx	xx.xx	xx.xx	xx.xx	xx.x	xx.x	xx	xx.xx	xx.xx	xx.xx	xx.x	xx.x
	TIME POINT 3	xx	xx.xx	xx.xx	xx.xx	xx.x	xx.x	xx	xx.xx	xx.xx	xx.xx	xx.x	xx.x
	...	...	...	...	...	...	...	...	...	...	...	...	...
	<All other time points>	xx	xx.xx	xx.xx	xx.xx	xx.x	xx.x	xx	xx.xx	xx.xx	xx.xx	xx.x	xx.x

Note: The data in this table are presented in listing xx

All subjects were to receive both treatments (i.e., Regimen 6 and Regimen 7) in a randomised manner over the two separate dosing occasions

BASELINE is defined as Day 1, Pre-dose of the corresponding study period

PROGRAM PATH: X:\~\QSC207031\~\TFLS\PRODUCTION\TAB-XX

DDMMYYYY HH:MM

Programming note: This table will be continued for all ECG parameters, which will follow the order given in the RAP text  
A similar table will be produced for triplicate readings i.e., Table [14.5.2.2.2]

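### The SAP defines the Part 2 laboratory baseline inconsistently: section 11.4.1 uses one Day -1 value for both periods, section 3.2.3 requires a baseline for each dosing period

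*SAP*

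**What the plan says.** The SAP describes the laboratory baseline for Part 2 in three ways.

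- **General rule, SAP 3.2.3:** "Baseline is defined as nominally the last measurement recorded prior to the first dose of IMP, for each dosing period".
- **Laboratory text, SAP 11.4.1:** summaries "including changes from baseline (Admission, Day-1) at each scheduled post-baseline time point by treatment in Part 2". Mock Table 14.4.2.1, the Part 2 summary, repeats this under both the fasted and the fed blocks: "BASELINE is defined as Day -1, Admission".
- **Part 2 shift table, mock Table 14.4.2.2:** "BASELINE is defined as Day -1, Admission of the corresponding study period".

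Participants are dosed on Day 1 and Day 8 and, under Protocol 8.1.2, "will remain resident in the clinical unit until discharge on Day 12". The schedule therefore has one admission, on Day -1.

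The other Part 2 safety data have a baseline in each period. SAP 11.5.1 on vital signs has "change from baseline (Pre-dose, Day 1 (Period 1), Day 8 (Period 2), will be summarised", and the Part 2 ECG mock Table 14.5.2.2.1 has "BASELINE is defined as Day 1, Pre-dose of the corresponding study period".

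**The concern.** Change from baseline in laboratory safety tests is part of the primary endpoint. Under 11.4.1 and Table 14.4.2.1, every Period 2 laboratory change would be measured from a sample taken before the Period 1 dose, yet reported under the Period 2 regimen. A Period 1 change that had not resolved, or a drift over the inpatient stay (for example from repeated blood sampling), would then count towards the regimen given second.

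The two mock tables for the same parameter could also end up with different baselines. Part 2 is open-label, so a choice left until programming would be made with treatment known.

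**Working it through.** No sample size, power or significance level in the plan depends on this baseline, so there is no stated figure to reproduce. The check is a comparison of the definitions with the schedule, followed by the arithmetic of the consequence.

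**1. Definitions against the schedule**

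| Source | Period 1 baseline | Period 2 baseline |
|---|---|---|
| SAP 3.2.3 | last value before the Day 1 dose (Day -1) | last value before the Day 8 dose (Day 7) |
| SAP 11.4.1, mock Table 14.4.2.1 | Day -1 | Day -1 |
| Mock Table 14.4.2.2 | Day -1 | Day -1, admission, of Period 2; no such admission is scheduled |
| Vital signs and ECG, for comparison | Day 1 pre-dose | Day 8 pre-dose |

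The time-point tables (Protocol Appendix 6, SAP Appendix 5) schedule Period 1 laboratory samples at 24 h, 96 h and 144 h. The 144 h sample falls on Day 7. There is no laboratory sample on Day 8 before dosing, so Day 7 is the last one before the Period 2 dose.

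**2. Size of the effect under 11.4.1 as written**

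Inputs: 8 participants with balanced allocation (SAP 5.4), taken as 4 per sequence. F and S are the true fed and fasted changes, r is the share of a Period 1 change still present in the Period 2 values, and d is the common drift accrued between Day -1 and the start of Period 2. The documents give none of F, S, r or d. All are assumptions, with r between 0 and 1.

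- Fed mean = [4F + 4(F + rS + d)]/8 = F + (rS + d)/2
- Fasted mean = [4S + 4(S + rF + d)]/8 = S + (rF + d)/2
- Fed minus fasted = (F − S)(1 − r/2)

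Illustration with F = 10 and S = 0:

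| r | d | Fed | Fasted | Difference |
|---|---|---|---|---|
| 0 | 0 | 10 | 0 | 10 |
| 0.25 | 0 | 10 | 1.25 | 8.75 |
| 0.5 | 0 | 10 | 2.5 | 7.5 |
| 1 | 0 | 10 | 5 | 5 |
| 0 | −4 | 8 | −2 | 10 |

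Drift moves both columns by d/2 and cancels in the difference.

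**3. Is drug carry-over likely?**

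The doses are 168 h apart and the predicted half-life is 19 h (Protocol 5.3.1.2). That is 168/19 = 8.8 half-lives, leaving 0.5^8.8, about 0.22% of the drug. Assumed half-lives of 30, 40 and 60 h would leave 2.1%, 5.4% and 14.4%. A laboratory change can outlast the drug, so these figures do not fix r, but they give no reason to expect it to be large.

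**4. Behaviour of a Day 7 baseline**

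Let r7 be the share of the Period 1 change still present at Day 7. The drift accrued by Day 7 drops out, and each regimen's mean moves by (r − r7)/2 times the other regimen's effect. This is zero if the residual is stable (r = r7). If it is resolving, with assumed r7 = 0.5 and r = 0.1, the shift is (0.1 − 0.5)/2 = −0.20 times the other effect. A Day -1 baseline would give 0.1/2 = +0.05.

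**5. The shift-table footnote read literally**

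If Period 2 has no baseline value, SAP 11.4.1 bases shift percentages only on participants with both a baseline and a post-baseline value, so 4 of 8 would drop out of each column. Alternatively, SAP 14.1 allows imputation of a missing baseline from a preceding time point and names screening and admission as examples, which could lead back to Day -1.

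**The case against.** The sentence in 11.4.1 is one generic label covering all three parts, two of which have a single period. A reader might infer that the SAP has decided on Day -1 for both periods. The documents do not settle that, because 3.2.3 states the opposite in general terms. What stands is a contradiction, and a programmer could reasonably follow the laboratory-specific text.

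The shift-table footnote may be less wrong than it looks. Protocol 11.2 numbers days within a period, and the Part 2 vital-sign and ECG footnotes use Day 1 of the corresponding period to mean study Day 8. Read the same way, Day -1 of Period 2 is study Day 7, which has a laboratory sample and agrees with 3.2.3. Only the word Admission does not fit. It therefore cannot be said that the shift tables necessarily share the problem in 11.4.1.

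A reader might also infer that Period 2 results do carry over Period 1 effects. No passage shows this. It requires a change that outlasts the washout, and SAP 5.1.2 allows the washout to be extended on Part 1 PK.

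Safety interpretation has other supports, none of which depends on the baseline label in 11.4.1: listings of individual values with high and low flags (SAP 11.4.2), reporting of clinically significant abnormalities as adverse events (Protocol 14.5.10), and assignment of adverse events by period (SAP 11.3).

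Finally, Day 7 is not an unexposed reference, as step 4 of the working shows. That objection stands as a caveat on the fix. It does not remove the need for one definition.

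**Conclusion.** The inconsistency is on the face of the SAP and should be corrected. Under 11.4.1 as written, each regimen's mean laboratory change can move by (r × the other regimen's effect + d)/2. With r unknown between 0 and 1, that is from none to half of the other regimen's effect, plus half of any drift. The result assumes 4 participants per sequence, and the bias vanishes if r and d are both zero.

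A reader might take the factor (1 − r/2), for example a 25% shrinkage at r = 0.5, as damage to a food-effect result. The documents do not support that: r = 0.5 is an assumption, laboratory data are only summarised descriptively by treatment, and the formal Part 2 analysis (SAP 9.6.2) covers PK parameters only. This is a low-cost correction to descriptive tables that feed the primary safety endpoint. No test, sample size or dose decision changes.

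**What to change.** In SAP 11.4.1 and mock Tables 14.4.2.1 to 14.4.2.4, apply 3.2.3 explicitly:

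- Period 1 baseline: the Day -1 admission sample.
- Period 2 baseline: the last laboratory sample before the Period 2 dose, which is Day 7 (144 h) as scheduled, or the last pre-dose sample if the washout is extended.

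Add a note that if a Period 1 change is still resolving at Day 7, the Period 2 baseline carries some of it and the tables should be read accordingly.

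The cost is SAP wording and table footnotes. No new sample is needed, because Day 7 is already in both schedules. In the same edit, reconcile the first Period 2 laboratory time point, which is 48 h (Day 10) in Protocol Appendix 6 but 24 h (Day 9) in SAP Appendix 5.

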##### **11.4.2 Listings for Laboratory Evaluations**

For each study part, the sample collection data (e.g., collection times) for laboratory analysis and urinalysis data will be listed.

All individual participant data, for planned haematology, clinical chemistry and urinalysis data including derivations, such as change from baseline, will be listed. If applicable, data from unscheduled laboratory tests will also be listed and flagged with a "#" to indicate it will not be used in the summary statistics. In these listings, individual data will be flagged with an "H" or an "L" for values that are higher or lower than their reference ranges, respectively.

Separate listings of all haematology, coagulation, clinical chemistry and urinalysis values outside their reference ranges by participant will also be provided. Reference ranges will be supplied by the safety laboratory for haematology and clinical chemistry and per the eCRF for urinalysis (i.e., a positive or negative result) with the exception of the following reference ranges for urinalysis:

- pH: 5.0 to 9.0

**Sponsor/Quotient Sciences Confidential**

---

- Specific gravity: 1.000 to 1.030

## 11.5 Vital Signs

For each study part, the details of measurement of supine vital signs (i.e., systolic and diastolic BP, and heart rate) and non-supine vital signs (oral temperature and respiratory rate) will be measured at each scheduled timepoint.

Systolic and diastolic BP and heart rate orthostatic measurements will also be taken (1 supine and 1 standing) according to the time schedules presented in [Appendix 4](#) (Part 1), [Appendix 5](#) (Part 2) and [Appendix 6](#) (Part 3). Vital signs parameters will be reported in the order given above, i.e., both summary tables and data listings.

### 11.5.1 Summary Tables for Vital Signs

For each study part, vital signs data (including orthostatic measurements), and change from baseline (Pre-dose, Day 1 (Period 1), Day 8 (Period 2), will be summarised (i.e., n, mean, SD, median, minimum and maximum) at each post-baseline time point by treatment in Part 2, and by all placebo, all active and each dose level in Part 1 and Part 3.

In addition, the number of subjects with 'substantial' increases or decreases or no substantial change from baseline in systolic BP (>20 mmHg), diastolic BP (>10 mmHg) and heart rate (>15 bpm) will be summarised.

Orthostatic hypotension will also be investigated at each time point. The change in systolic BP and diastolic BP between the mean of the duplicate supine measurements and the subsequent standing measurement will be calculated for each subject (i.e., standing BP- Supine BP) and summarised (i.e., mean, SD, median, minimum, maximum and n) at baseline and each post-baseline time point.

In addition, the number of subjects with 'substantial' decreases or no substantial decrease from supine to standing results in systolic BP (>20 mmHg) and diastolic BP (>10 mmHg) will be presented at each time point.

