#### **8.5 Stopping Criteria**

##### **Cohort stopping rules**

Dose escalation, as well as continued dosing within any given cohort, will be paused and may be halted based on full review of all available clinical safety data if any of the following occur:

- Two or more participants in the same cohort experience an AE assessed as severe
- Two or more participants with QTcF >500 msec and/or an increase in QTcF >60 msec considered related to IMP administration
- At least 2 participants in the same cohort with demonstrated recurrent or persistent post-dose orthostatic hypotension (i.e., either a drop of systolic blood pressure [SBP]  $\geq$ 20mmHg or diastolic blood pressure [DBP]  $\geq$ 10mmHg after 3 min standing) and/or symptomatic hypotension (lightheadedness, weakness, blurry vision, dizziness or fainting upon standing) requiring medical intervention

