**14.6 Vital Signs Measurements**

Blood pressure and heart rate will be measured by an automated recorder after the participant has been in a supine position for a minimum of 5 min and oral temperature and respiratory rate will be measured according to the time schedules presented in [Appendix 2](#)[Appendix 5](#), [Appendix 6](#) and [Appendix 7](#).

Blood pressure and heart rate orthostatic measurements will also be taken according to the time schedules presented in [Appendix 5](#), [Appendix 6](#) and [Appendix 7](#). Two measurements will be recorded; 1 supine and 1 standing. The first supine measurement will be performed after the participant has rested in a supine position for at least 5 min. The second blood pressure and heart rate measurements will be performed after the participant has been standing for at least 3 min but no more than 5 min. Orthostatic hypotension will be defined as either:

- A decrease of SBP  $\geq$  20 mmHg after 3 min standing, or
- A decrease of DBP  $\geq$  10 mmHg after 3min standing

The acceptable deviations from the nominal vital signs measurement time points are:

- Day 1 in all parts and Day 8 in Part 2: The pre-dose vital signs measurements will be taken  $\leq$  2 h before dosing
- On Days 2 and 3 (Part 3 only): the pre-dose vital signs measurements will be taken  $\leq$  1 h before dosing.
- Post-dose vital signs measurements will be taken  $\pm$  15 min from the nominal post-dose time point.
- For return visits, vital signs measurements will be taken  $\pm$  2 h from the nominal return visit time point.
- End of study visit vital signs measurements will be taken  $\pm$  1 day from the nominal time point.

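### SAP 11.5.1 counts supine-to-standing falls with strict cut-offs, so a fall of exactly 20 mmHg systolic or 10 mmHg diastolic meets the protocol's definition of orthostatic hypotension but goes uncounted

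*SAP*

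**What the plan says.** Protocol 14.6 describes the orthostatic procedure and gives a definition. On the readings it says: "Two measurements will be recorded; 1 supine and 1 standing". Orthostatic hypotension is then met by either of two criteria. The first is "A decrease of SBP $\geq$ 20 mmHg after 3 min standing, or" and the second is the matching diastolic criterion, also inclusive, at 10 mmHg. The cohort stopping rule in protocol 8.5 uses the same inclusive limits and applies to "At least 2 participants in the same cohort with demonstrated recurrent or persistent post-dose orthostatic hypotension". Exclusion criterion 5 in protocol 9.3 uses the same limits for eligibility at screening in Parts 1 and 3.

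SAP 11.5 repeats the protocol's procedure: "heart rate orthostatic measurements will also be taken (1 supine and 1 standing". SAP 11.5.1 then states: "Orthostatic hypotension will also be investigated at each time point". It does this in two ways:

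- It summarises the continuous change "between the mean of the duplicate supine measurements and the subsequent standing measurement will be calculated for each subject".
- It counts participants with and without a substantial "decrease from supine to standing results in systolic BP (>20 mmHg) and diastolic BP (>10 mmHg" at each time point.

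SAP 13.2 declares no change to the planned analyses.

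**The concern.** The protocol and the SAP disagree in three respects about what counts as a case: the inequality (inclusive against strict), the combination rule (either criterion against each parameter separately), and the supine reference (one reading against the mean of two). None is explained, and SAP 13.2 says nothing has changed.

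Vital signs are part of the primary safety endpoint, and protocol 6.4.1 lists transient rises in heart rate and blood pressure among the potential risks and says that monitoring will include orthostatic evaluations. With 6 active participants per dose level, one participant is 1/6 = 17 percentage points of a dose-group rate. A report that shows a protocol-defined case as having no substantial decrease understates the finding at that dose. It may also fail to reconcile with participants identified under rule 8.5.

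**Working it through.** **No published figure to reproduce.** The SAP gives no expected frequency of orthostatic hypotension, so the check compares the two rules directly and then sizes the difference under stated assumptions.

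**Step 1: boundary cases.** Write a fall as systolic/diastolic in mmHg, using the same supine and standing readings for both rules. The protocol rule is systolic ≥20 or diastolic ≥10. The SAP rule is systolic >20 and diastolic >10, shown separately.

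| Fall | Protocol case | SAP systolic count | SAP diastolic count |
|---|---|---|---|
| 20/5 | yes | no | no |
| 19/10 | yes | no | no |
| 20/10 | yes | no | no |
| 21/10 | yes | yes | no |
| 20/11 | yes | no | yes |
| 21/11 | yes | yes | yes |
| 19/9 | no | no | no |

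The first three rows are protocol cases that appear on neither SAP count. No row is an SAP case without being a protocol case, so the inequality alone can only lower the count. This step needs no assumption.

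**Step 2: size of the loss from the inequality (assumptions, not document figures).** Assume that readings are whole mmHg and that the fall is normal with mean μ and standard deviation σ. With c = 20 (systolic) or 10 (diastolic):

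- protocol probability: P(fall ≥ c) = 1 − Φ((c − 0.5 − μ)/σ)
- SAP probability: P(fall > c) = 1 − Φ((c + 0.5 − μ)/σ)
- share missed = 1 − SAP/protocol

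Example with σ = 8 and μ = 0:

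- Systolic: (19.5 − 0)/8 = 2.4375 gives 0.74%, and (20.5 − 0)/8 = 2.5625 gives 0.52%. The difference is 0.22 percentage points, or 30% of the qualifying falls.
- Diastolic: 9.5/8 = 1.1875 gives 11.8%, and 10.5/8 = 1.3125 gives 9.5%. The difference is 2.3 percentage points, or 19%.

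For a mean fall between −5 and +3 mmHg (negative means a rise on standing):

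| σ (mmHg) | Systolic share missed | Systolic difference (pp) | Diastolic share missed | Diastolic difference (pp) |
|---|---|---|---|---|
| 8 | 27-35% | 0.04-0.52 | 16-25% | 0.9-3.4 |
| 10 | 19-25% | 0.18-0.94 | 12-18% | 1.3-3.1 |

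Multiplying each difference by 6 active participants gives the expected number of exact-boundary falls per cohort per time point: about 0.002 to 0.06 systolic and 0.05 to 0.20 diastolic.

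For the either/or definition, a simulation was run over wider assumptions: mean falls 0 to 10 mmHg systolic and −5 to +3 mmHg diastolic, SD 8 to 10 and 6 to 8 mmHg respectively, and correlation 0.3 or 0.6. It gave 17% to 33% of protocol-defined cases missed at a time point.

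**Step 3: the supine reference.** Protocol 14.6 and SAP 11.5 give one supine reading, while SAP 11.5.1 averages two. To see what averaging would do if two readings existed, systolic falls were simulated with mean 5 and SD 10 mmHg, within-person supine SD 3 to 5 mmHg, and the inclusive cut-off held fixed. Compared with a single reading, 20% to 30% of cases were lost. New cases equal to 10% to 14% of the single-reading count were gained. Averaging therefore reclassifies in both directions, and the one-way loss in Step 1 comes only from the inequality.

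**The case against.** The strongest reply is that this affects one dichotomised descriptive row. SAP 11.5.1 also summarises the continuous change, including minimum and maximum, so the largest fall stays visible. SAP 11.5.2 lists every individual orthostatic value, and protocol 14.6 requires any clinically significant abnormality to be reported as an adverse event. The row is labelled a substantial decrease and reuses the blood-pressure cut-offs of the change-from-baseline convention. The protocol sets no orthostatic incidence endpoint, no test or sample size depends on the row, and the percentages rest on assumed distributions with a small systolic base.

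Most of this stands and limits the severity. It does not remove the point. The row is the SAP's only count on orthostatic hypotension, in a paragraph that names that condition. The increase and decrease flags in SAP 11.5.2 cover change from baseline only, so a reader of the listings gets no flag on a boundary fall. The vital-signs mock tables likewise define substantial change from baseline only.

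A reader might infer three stronger things that the documents do not support:

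- **That the stopping rule is weakened.** Rule 8.5 is applied to clinical data during the study, and the SAP table plays no part in it. The rule also requires recurrence or persistence, or symptoms, and counts participants per cohort. A per-time-point row would not match it exactly even with identical cut-offs.
- **That cases vanish from the record.** They are missing from the count but not from the listed data.
- **That the duplicate mean also loses cases, or cannot be computed.** Step 3 shows movement both ways. In Part 1 (protocol Appendix 5), routine and orthostatic vital signs share the pre-dose, 2, 4, 12, 24 and 144 h time points, so a second supine reading might exist. The SAP does not say that it would be used.

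**Conclusion.** The concern holds as a reporting inconsistency. As written, SAP 11.5.1 places falls of exactly 20 mmHg systolic or exactly 10 mmHg diastolic in the no-substantial-decrease category, although protocol 14.6 defines them as orthostatic hypotension. It never gives the number of participants meeting either criterion. The direction is certain for a fixed pair of readings.

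The size is not certain. The relative losses of 19-35% (systolic) and 12-25% (diastolic) depend on whole-mmHg readings, normality, and assumed means and SDs; the protocol says only that an automated recorder is used. The absolute effect is below 1 percentage point for systolic and about 1 to 3 points for diastolic falls per time point. The table may fail to reconcile with participants identified under rule 8.5, but it need not. The duplicate supine mean is a separate contradiction, both with the protocol and within the SAP, and its net effect cannot be signed from the documents.

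This should be fixed. No dose decision, test or sample size turns on it.

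**What to change.** In SAP 11.5.1:

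1. For the supine-to-standing change only, replace the strict cut-offs with the inclusive ones of protocol 14.6 (≥20 mmHg systolic, ≥10 mmHg diastolic). The separate change-from-baseline cut-offs need not change.
2. Take the change from the single supine reading described in protocol 14.6 and SAP 11.5. If a second supine reading is intended, say which one and record the departure in SAP 13.2.
3. Add one row per time point counting participants who meet either criterion, with a mock table for the supine-to-standing results.

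The cost is a few words of SAP text, one table row and its shell. No additional data are needed. For the same readings, the reported count can only stay the same or rise when the cut-offs change. The amendment should be made before database lock and unblinding, so that the case definition is not chosen with the results in view.
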